A Introduction

A1 Study Abstract:

This study will use non-invasive MR scanning to help answer questions related to brain function and development in children suffering from craniosynostosis. Craniosynostosis affects roughly 1 in 2000 children. Primary indication for operative treatment for patients with craniosynostosis is to prevent or treat increased Intra-Cranial Pressure (ICP) and avoid neurological impairment. Increased ICP is thought to result from restricted space for brain growth caused by the abnormal cranial vault. However, the literature on the relationship between craniosynostosis and ICP is limited. Due to the invasiveness of the test, preoperative ICP monitoring is not routinely performed to decide if operative repair is required. Other indirect signs of elevated ICP have been described but are not reliable.

While it is not currently feasible to measure ICP directly, we may be able to indirectly determine ICP in children via magnetic resonance imaging (MRI). We aim to compare the assessment of ICP with the conventional, invasive intraventricular shunt to an indirect assessment of ICP via MRI.

Ten children with an intraventricular shunt will be enrolled in this pilot study over a one-year period. We will obtain indirect measures of ICP. The results will be compared to ICP measures obtained via the shunt.

Ultimately the assessment of ICP using MRI in patients with craniosynostosis may revise surgical indications and timing of surgery, potentially changing the standard of care for patients with craniosynostosis. Additionally, this approach might be used for patients with other diagnoses which impact ICP.

A2 Primary Hypothesis

Indirect (via MRI) and direct measures of ICP will have a significant positive correlation.

A3 Purpose of the Study Protocol

The purpose of this study is to evaluate the use of magnetic resonance imaging (MRI) to determine intra-cranial pressure in young children.

B Background

B1 Prior Literature and Studies

Literature is limited on the relationship between craniosynostosis and ICP. The most widely reported study is by Renier and colleagues.¹ In 75 patients preoperative ICP monitoring was performed using an epidural sensor. They identified ICP to be normal in one-third of the cases, obviously elevated in one-third, and borderline in one-third. When counseling patients, practitioners report a 13% rate of increased ICP for single suture synostosis and 42% for multiple suture synostosis. However, the authors used adult normative values for ICP (normal less than 10mmHg and elevated greater than 15mmHg). Normal ICP in children and infants has been identified to be closer to 6 mmHg.²

B2 Rationale for this Study

Currently all patients with craniosynostosis are treated surgically due to concern that the abnormal cranium restricts the brain, causing increased ICP. However, due to the invasiveness and potential harm of the current approach, ICP is rarely measured in patients with craniosynostosis. Accurate measures of ICP using MRI in patients with craniosynostosis may revise surgical indications and timing of surgery, potentially changing the standard of care for patients with craniosynostosis. This would allow family members of patients with craniosynostosis to be more informed as to the indication for operative repair, i.e., decreased brain metabolic activity and/or cosmetic.

Our research may ultimately provide a tool for practitioners to not only identify which patients need to be treated, but also show adequate surgical therapy with resolution of ICP. Some patients, particularly those with syndromic craniosynostosis, require a secondary operation at an older age to expand cranial volume. The decision to perform a secondary operation is based on clinical signs and symptoms. Development of non-invasive techniques to identify ICP will also inform this process and allow for early and correct identification of patients who need surgical treatment.

C Study Objectives

C1 Primary Aim

To evaluate ICP through the use of magnetic resonance (MR) imaging techniques in patients under the age of eight years old.

C2 Rationale for the Selection of Outcome Measures

Although multiple tests have been suggested to assess ICP in patients with craniosynostosis, including papilledema and copper beaten appearance of the skull on plain film, none have been shown to be reliable measures or markers of ICP. Recent advances in MRI suggest that ICP can be indirectly measured with this modality non-invasively and with minimal patient risk.

D Investigational Agent

D1 Clinical Data to Date

The MR sequences for this study have been used in studies of traumatic brain injury. To our knowledge these sequences have not yet been used for patients with craniosynostosis.

D2 Dose Rationale and Risk/Benefits

The main risk of the MR scan in this population is the feeling of being closed in or discomfort from lying still. This is an acceptable risk given the benefit of obtaining hard evidence of brain stress in subjects with synostosis. The time patients are in the scanner (approximately 45 minutes) has been adequate to obtain useful data in populations of minors post traumatic brain injury and normal controls. These tests were performed by Drs. [name] and [name].⁷

E Study Design

E1 Overview or Design Summary

Up to 12 patients with craniosynostosis will be enrolled in this pilot study. Various measures of cerebral metabolism and perfusion will be taken during a single visit via MR scanning.

The results may also be compared to age and gender matched normative data. These controls will be recruited in the plastic surgery clinic and/or deidentified data from normal subjects from another study will be used. Participation in this research study consists of one to two parts. First, all patients will be asked to extend a clinical visit for MRI. During this time the intra-cranial pressure MRI testing will be done, lasting approximately 10 minutes. The scan will be performed in the radiology center on the 1st floor of Children's Hospital. The clinical scan will be done under sedation. Secondly, during the same visit, a transducer will be attached to the participant's intraventricular catheter if it is not already in place. The patients ICP will be measured directly with this transducer. Subjects have no further commitment once the scan (and ICP measurement) is complete.

E2 Subject Selection and Withdrawal

2.a Inclusion Criteria

- Subjects presenting to the Plastic Surgery clinic with unrepaired single-suture craniosynostosis.
- Age-matched controls

Exclusion Criteria

- Implants (e.g. pacemakers) that might rule out use of MR scanning.

- History of other abnormalities known to affect brain topology or function.
- Control subjects must have no history of craniofacial abnormality or head trauma.

2.b Subject Recruitment Plans and Consent Process

Subjects will be recruited through the Plastic Surgery clinic.

2.c Risks and Benefits

Risks: the risk of discomfort of claustrophobia during the MR scan

Benefits: Future patients with craniosynostosis might benefit from this study because it may lead to a revision of surgical indications and timing of surgery, potentially changing the standard of care for patients with craniosynostosis.

2.d Early Withdrawal of Subjects

Subjects may withdraw at any time before or during the study.

2.e When and How to Withdraw Subjects

Subjects or their parents/guardians may withdraw verbally.

2.f Data Collection and Follow-up for Withdrawn Subjects

There will be no follow-up data collection

F Study Procedures

F1 Screening for Eligibility

Craniosynostosis will be diagnosed via computed tomography performed as part of standard care

F2 Schedule of Measurements

There will be a single visit consisting of the MR scan, performed in the Center for Clinical Imaging Research.

F3 Safety and Adverse Events

3.a Medical Monitoring

Prior to MR scanning, subject's parent or guardian will complete an MRI safety questionnaire. The subject's heart rate and blood pressure will be continuously monitored and recorded every 15 minutes during the MR scan.

3.b Definitions of Adverse Events

Typical adverse events during MR scans are claustrophobia and issues relating to metallic implants.

3.c Data Collection Procedures for Adverse Events

Any adverse events will be duly recorded and noted by the investigators

3.d Reporting Procedures

A summary of any adverse events will be included in continuing review forms sent to the IRB.

3.e Adverse Event Reporting Period

Annually (in the continuing review forms)

F4 Study Outcome Measurements and Ascertainment

MR spectroscopy (MRS) will be used to obtain concentrations of N-acetyl aspartate (NAA) and lactate. NAA is a highly sensitive marker of brain injury and the presence of lactate can indicate compromised metabolism. We will measure whole-brain oxygen extraction (OEF) using a magnetic field mapping approach. Elevated OEF is a key indicator of compromised perfusion. Cerebral blood flow (CBF) will be measured using an arterial spin labeling (ASL) sequence, which will allow direct measurement of perfusion deficiencies. We will also obtain functional connectivity data using an rfcMRI sequence, which is sensitive to developmental delay. The analysis for OEF and ASL data will be performed by [name]. The MRI images will be read by [name], Chief of Radiology at Saint Louis Children's Hospital. Measures will include location and severity of metabolic effects, size of the optic nerve sheath, and cerebral perfusion.

G Statistical Plan

G1 Sample Size Determination and Power

As this is a pilot study there is no relevant data to determine the power of this study. The data collected here will be used as a guide for sample size determination of future studies.

G2 Interim Monitoring and Early Stopping

N/A

G3 Analysis Plan

The data obtained from the pilot study will be evaluated for patterns in the data between the subjects with craniosynostosis and the matched controls.

G4 Statistical Methods

Various graphical and image analysis approaches will be applied to tease out potential patterns between cases and controls and between the affected and unaffected sides of patients with unilateral craniosynostosis.

H Data Handling and Record Keeping

H1 Confidentiality and Security

Privacy during the recruitment and consent process will be protected by performing these procedures in private patient rooms in the hospital or clinic setting.

The MRI will be performed in the Center for Clinical Imaging Research (CCIR). No unnecessary PHI will be collected. Data will be a coded.

H2 Training

All members of the research team will be familiar with this protocol and the standard prosecution of clinical trials.

H3 Records Retention

Patient records will be stored behind a double lock system in the craniofacial laboratory in the division of Plastic Surgery.

I Study Administration

I1 Organization and Participating Centers

Division of Plastic Surgery in cooperation with the Department of Radiology

I2 Funding Source and Conflicts of Interest

None at this time.

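### Section G plans no analysis of the primary hypothesis (MRI against direct ICP), no MRI variable is named as the indirect ICP measure, and a significant correlation alone would say little about how well MRI determines ICP

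*Combined protocol and SAP*

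**What the plan says.** **Question and hypothesis.** A3 gives the purpose as "to evaluate the use of magnetic resonance imaging (MRI) to determine intra-cranial pressure in young children". A2 states the primary hypothesis: "Indirect (via MRI) and direct measures of ICP will have a significant positive correlation". It gives no type of coefficient, alpha, sidedness or minimum size.

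**Paired readings.** A1 says "Ten children with an intraventricular shunt will be enrolled in this pilot study over a one-year period" and, of the MRI results, "The results will be compared to ICP measures obtained via the shunt". E1 describes the MRI part ("During this time the intra-cranial pressure MRI testing will be done, lasting approximately 10 minutes") and, at the same visit, a transducer on the intraventricular catheter: "The patients ICP will be measured directly with this transducer".

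**Who is studied.** E1 says "Up to 12 patients with craniosynostosis will be enrolled in this pilot study" and "Participation in this research study consists of one to two parts". E2 admits children with single-suture craniosynostosis and age-matched controls. It has no shunt or catheter criterion, and it excludes other abnormalities that affect the brain.

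**MRI measures.** F4 lists NAA, lactate, oxygen extraction, cerebral blood flow, functional connectivity and optic nerve sheath size. None is identified as the indirect measure of ICP. E1 does not describe the output of its ten-minute test.

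**Analysis.** G3 looks for patterns between craniosynostosis subjects and matched controls. G4 adds affected against unaffected sides, by graphical and image analysis. G1 says that the data will guide the sample size of later studies.

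**The concern.** The hypothesis, the purpose and the analysis do not line up. A2 and A3 concern the relation between two readings in the same child. Neither comparison in G3/G4 uses that pairing, so an analyst who followed section G exactly would never test A2.

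Two further gaps follow. With several MRI measures and about ten children, an indirect ICP measure chosen after the data are seen would make a significant result hard to interpret. And even if A2 were tested as worded, significance of r is a weak answer to A3, because it does not say how far an MRI-based value lies from the direct one. The later studies that G1 has in mind would then inherit no planned estimate of error.

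**Working it through.** The plan has no figure to reproduce: G1 gives no power calculation, and ten and up to 12 are stated without derivation.

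**1. Is A2 analysed anywhere in section G?**

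| Section | Comparison | Uses MRI–direct ICP pairs? |
|---|---|---|
| A1, A2, E1 | MRI against direct ICP, same child | Yes (intent and data) |
| G3 | Cases against matched controls | No |
| G4 | Cases against controls; affected against unaffected side | No |

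Section G contains no correlation, regression, calibration or agreement analysis of MRI against direct ICP.

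**2. What would a significant r show?** Inputs: n = 10 pairs (A1). Assumed, because not stated: Pearson correlation and two-sided alpha 0.05.

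- Smallest significant r = t/√(n − 2 + t²), with t(0.975, 8) = 2.306: 2.306/√(8 + 5.318) = 0.632.
- r² = 0.40, so about 60% of the variance in direct ICP is unexplained.
- Fisher z 95% CI: tanh(0.745 ± 1.96/√7) = 0.004 to 0.90.
- Residual SD / ICP SD = √((1 − r²)(n − 1)/(n − 2)) = √(0.601 × 9/8) = 0.82.

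Sensitivity to the assumptions:

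| Pairs, test | Just-significant r | Variance unexplained (1 − r²) |
|---|---|---|
| 12, two-sided | 0.576 | 67% |
| 10, two-sided | 0.632 | 60% |
| 10, one-sided | 0.549 | 70% |
| 8, two-sided | 0.707 | 50% |
| 6, two-sided | 0.811 | 34% |

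The documents give no SD for ICP, so the residual SD cannot be put in mmHg without a further assumption.

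**3. Bias, only if the MRI output is in mmHg.** MRI = direct + 8 and MRI = 2 × direct both give r = 1. Correlation sees neither constant nor proportional error.

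**4. Precision of an error estimate at n = 10.**

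- Residual SD, 95% CI as a multiple of the estimate, √(df/χ²) with df = 8: √(8/17.535) = 0.68 to √(8/2.180) = 1.92. At n = 12 it is 0.70 to 1.75; at n = 6, 0.60 to 2.87.
- Each limit of agreement, 95% CI half-width in SDs of the differences, t(0.975, 9) × √(1/n + 1.96²/(2(n − 1))): 2.262 × √(0.100 + 0.213) = 1.27. At n = 12 it is 1.12; at n = 6, 1.91.

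**The case against.** **The comparison is already intended.** A1 announces it, A2 names correlation and E1 collects the direct reading. A reader might infer that the study never meant to set MRI against direct ICP, or cannot do so. The documents do not support that: what is missing is the planned method, not the intent or the measurement.

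**A2 is a hypothesis, not a decision rule.** This stands. The threshold of 0.632 depends on an alpha, a coefficient and a number of pairs that I supplied. It is also the weakest result that would pass: at r = 0.8 the unexplained share is 36% (1 − 0.64), and at r = 0.9 it is 19% (1 − 0.81). The figure shows what significance permits, not what is expected.

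**Correlation suits markers on another scale.** This stands in part. The measures named in F4 are not pressures, and constant bias has no meaning for them. A reader might infer that A2 necessarily hides a bias in mmHg, but that holds only if E1's ten-minute test yields mmHg, which the documents do not say. For a marker in its own units, the residual SD follows from r, n and the ICP SD, so the gain there is mainly better reporting. But section G does not plan r either.

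**A pilot may leave accuracy to later work.** Testing association first is reasonable, and the lack of a power calculation is no fault here. Pilot status does not explain why the primary hypothesis has no analysis.

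**Catheters.** A reader might infer that no part of the plan requires one. That fits E2 only; E1 presupposes a catheter.

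**Conclusion.** The point holds. Section G as written leaves A2 untested, and no MRI variable is designated as the indirect ICP measure. Both follow from the text and need no assumption.

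The second limb is more limited. A significant r by itself would say little about A3: under Pearson, two-sided 0.05 and ten pairs, it can be reached with about 60% of ICP variance unexplained and a CI that starts at 0.004. Blindness to bias adds to this only if the MRI output is in mmHg.

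It would go too far to say that the remedy settles whether MRI can determine ICP. With about ten pairs it yields an association and an imprecise error. The number of pairs is itself uncertain and could be below ten while A1, E1 and E2 disagree. This should be corrected before the data are analysed.

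**What to change.** In G3/G4:

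1. Name one MRI measure in advance as the indirect ICP measure, either the output of E1's ten-minute test or one F4 measure, with its units. Treat the others as exploratory.
2. In patients with both readings, report r with its 95% CI. If a p-value is kept, state the coefficient, alpha and sidedness.
3. If the measure is in mmHg, add the mean difference and 95% limits of agreement with CIs, and check for proportional bias. Otherwise regress direct ICP on it and report the residual SD in mmHg with its chi-square CI on n − 2 df.
4. Limit the conclusion to association plus an estimated, imprecise error to guide the later studies in G1.

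Separately, reconcile A1 (ten shunted children), E1 (up to 12 craniosynostosis patients, a catheter presupposed, one or two parts) and E2 (no catheter criterion, other brain abnormalities excluded). Then state the expected number of pairs.

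**Cost.** No measurement beyond the pairs already planned, one paragraph in section G and a short analysis. The investigators must commit to one measure, and the rest lose confirmatory standing. The wide intervals will look less favourable than a bare p-value. Reconciling the population is a separate task that the added paragraph does not solve.

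### The plan compares cases with controls on perfusion, oxygen extraction and connectivity without recording or using sedation state, although E1 suggests that cases may be scanned sedated and nothing is said about controls

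*Combined protocol and SAP*

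**What the plan says.** Sedation is mentioned once, in E1: "The clinical scan will be done under sedation". The same paragraph ties the research imaging to that visit: "First, all patients will be asked to extend a clinical visit for MRI", and then "During this time the intra-cranial pressure MRI testing will be done, lasting approximately 10 minutes". It does not say whether the research sequences run while the child is still sedated.

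On controls, E1 says: "The results may also be compared to age and gender matched normative data", and "These controls will be recruited in the plastic surgery clinic and/or deidentified data from normal subjects from another study will be used". Age and gender are the only matching factors. Under E2, the one control-specific exclusion concerns craniofacial abnormality and head trauma. No section gives the sedation state of either control source.

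F4 lists CBF by arterial spin labeling, whole-brain OEF and functional connectivity among the measures. G3 consists of a search for patterns between cases and matched controls. G4 repeats that and adds a comparison of affected and unaffected sides in unilateral cases. Neither contains a restriction, stratum or covariate for sedation. G1 says that the pilot data will guide the sample size of later studies, without naming an endpoint.

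**The concern.** A case-control contrast needs the two groups to be measured under the same conditions, or the difference in conditions to be known. E1 makes it plausible that cases are imaged as an add-on to a sedated clinical scan. Control children recruited in clinic are not said to have a sedated scan to extend, and archived data were acquired under another study's procedures. The age and gender match does nothing about this.

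CBF, OEF and connectivity are physiological readouts. If sedation moves them, a group difference in sedation would show as a group difference in the measure and could be read as disease; F4, for instance, treats raised OEF as a sign of compromised perfusion. If the state is not recorded, an analyst could neither detect nor repair this afterwards, and a future study sized from that contrast would inherit the error.

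**Working it through.** **Step 1. What can be established about sedation state.** The text points both ways for cases.

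- Towards sedated: E1 attaches the research imaging to the visit with the sedated clinical scan. Section 3.a has heart rate and blood pressure monitored continuously and written down every 15 minutes, which fits sedation but does not state it.
- Towards awake: D2 says "The main risk of the MR scan in this population is the feeling of being closed in or discomfort from lying still". Sections 2.c and 3.b add only claustrophobia and implants. No sedation risk is listed.
- Unclear which scan is meant: E1 gives about 10 minutes in the hospital radiology center. D2 says "The time patients are in the scanner (approximately 45 minutes) has been adequate to obtain useful data", and F2 and H1 place the scan in the Center for Clinical Imaging Research. A1 adds a different population: "Ten children with an intraventricular shunt will be enrolled in this pilot study over a one-year period". The sedated 10-minute visit may belong to those children and the F4 measures to a separate scan.

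For controls there is no text on either side. The state of cases is therefore unresolved and that of controls unknown.

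**Step 2. When the effects can be separated.** Take a model with an intercept, a case indicator and a sedation indicator.

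- All cases and no controls sedated: the two indicators are the same column, so the design matrix has rank 2 of 3. Case and sedation effects are aliased at any sample size.
- All cases and half the controls sedated (equal groups): rank 3, with the variance of the case effect multiplied by 1.5. Separation is possible in principle, but only if sedation is recorded and used.

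**Step 3. Size of the bias.** The plan gives no effect size, SD or sedation effect, so there is no figure to reproduce. Assume a normal measure with equal SD, no disease effect, 12 cases (the E1 maximum) and a sedation shift of d SD. Let p be the share of cases sedated and q the share of controls sedated.

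- Bias in the mean difference = (p − q) × d.
- The control median m solves q × Φ(m − d) + (1 − q) × Φ(m) = 0.5.
- Expected cases beyond m, in the direction of the shift = 12 × [p × Φ(d − m) + (1 − p) × Φ(−m)].

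With awake controls (q = 0), m = 0. Using Φ(0.25) = 0.5987, Φ(0.5) = 0.6915 and Φ(1.0) = 0.8413:

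- p = 1: 12 × 0.5987 = 7.18; 12 × 0.6915 = 8.30; 12 × 0.8413 = 10.10.
- p = 0.5: 12 × (0.5 × 0.5987 + 0.25) = 6.59; 12 × (0.5 × 0.6915 + 0.25) = 7.15 (7.149 before rounding, so 7.1 to one decimal); 12 × (0.5 × 0.8413 + 0.25) = 8.05.

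With half the controls sedated (q = 0.5), m = d/2, so p = 1 gives 12 × Φ(d/2) and p = 0 gives 12 × Φ(−d/2).

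| Cases sedated (p) | Controls sedated (q) | Mean bias | d = 0.25 | d = 0.5 | d = 1.0 |
|---|---|---|---|---|---|
| equal to q | equal to p | 0 | 6 | 6 | 6 |
| half | none | +0.5d | 6.6 | 7.1 | 8.0 |
| all | half | +0.5d | 6.6 | 7.2 | 8.3 |
| all | none | +d | 7.2 | 8.3 | 10.1 |
| none | half | −0.5d | 5.4 | 4.8 | 3.7 |

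The last four rows are conditional on the assumed shifts. They show how the bias scales and are not evidence that sedation has an effect of that size.

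**Step 4. What is not exposed.** The A2 correlation relates MRI-based to direct ICP within patients and uses no controls. The G4 side comparison takes both sides from the same scan.

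**The case against.** Four arguments carry weight.

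- **The states may be equal.** Section 3.a describes one monitoring procedure for every subject scanned, and prospective controls come from the same clinic. If all are scanned in the same state, this bias is zero. That stands; the remaining defect is that the plan would not show it.
- **The harm is a chain of conditions.** The states must differ, sedation must shift the measure, the comparison must be made and, for the sizing harm, this contrast must be the one used. All true. On the third, E1 is permissive, but G3 states the comparison without condition and contains nothing else.
- **The analysis is already exploratory.** G3 and G4 plan graphical pattern-finding in up to 12 patients, with no test. This limits the consequence but does not remove it, because G1 intends the data to inform later studies. It does rule out one remedy: splitting about 12 cases by sedation state could leave near-empty cells.
- **The root may lie elsewhere.** The documents conflict on population, scan length and site, and settling that may settle the cases' sedation state. It would not settle the controls'.

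A reader might go further and infer that cases are sedated, controls are awake and every case-control pattern is hopelessly confounded. The documents do not support this. They state neither group's research-scan state, strict aliasing needs complete overlap of sedation with case status, and the argument made here covers CBF, OEF and connectivity, not NAA, lactate or optic nerve sheath size.

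**Conclusion.** The point holds in conditional form. E1 suggests but does not state that cases are scanned sedated, the controls' state is not given, and G3 and G4 compare the groups without recording or using it. If the states differ and sedation shifts CBF, OEF or functional connectivity, the contrast on those measures is biased by (p − q) × d. It is fully aliased when all cases and no controls are sedated; with partial overlap it is inseparable only because sedation is not recorded.

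The size ranges from no bias with equal states to the whole sedation effect under complete imbalance. It rests on the assumed shifts, a normal model with equal SD and 12 cases; no number of controls and no significance test is assumed. It would be wrong to read this as a threat to the primary hypothesis. The finding is a cheap improvement to the control comparison.

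**What to change.** - **E1:** add one sentence saying whether the research sequences are acquired under sedation.
- **Data collection:** record sedation state for every scan.
- **Control selection:** add sedation state to the criteria. Request it from the holder of any archived data, and prefer controls scanned in the same state as the cases.
- **G3:** restrict the case-control contrast on CBF, OEF and connectivity to like-state scans. Where states differ or are unknown, report the contrast as confounded by sedation and do not use it to size future studies.

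The cost is a sentence, one recorded item per scan, one data request and one analysis rule. It should be settled before scanning, since an unrecorded state may be hard to recover. The drawback is fewer usable controls: archived data may not hold sedation state, and the result may be only a descriptive contrast.

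### The primary hypothesis needs MRI and direct ICP in the same child, but eligibility, recruitment and screening define a population with no shunt or catheter condition, and the analysis plan contains no MRI-ICP correlation

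*Combined protocol and SAP*

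**What the plan says.** The opening sections describe a validation study.

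- A1: "Ten children with an intraventricular shunt will be enrolled in this pilot study over a one-year period". The MRI results are to be compared with ICP obtained through the shunt.
- A2, the primary hypothesis: "Indirect (via MRI) and direct measures of ICP will have a significant positive correlation".
- A3 gives the purpose as "to evaluate the use of magnetic resonance imaging (MRI) to determine intra-cranial pressure in young children".

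The operative sections describe a craniosynostosis cohort.

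- E1: "Up to 12 patients with craniosynostosis will be enrolled in this pilot study". Controls may be added. E1 also describes a transducer on the participant's intraventricular catheter and a direct ICP reading at the same visit. It says that taking part has either one or two parts.
- 2.a admits "Subjects presenting to the Plastic Surgery clinic with unrepaired single-suture craniosynostosis" and age-matched controls.
- 2.b recruits through the Plastic Surgery clinic only. F1 screens by a CT diagnosis of craniosynostosis.
- F2 schedules one visit made up of the MR scan.
- G3 and G4 look for patterns between cases and controls, and between affected and unaffected sides in unilateral disease.

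On how often direct ICP is available in this disease, A1 says that "preoperative ICP monitoring is not routinely performed to decide if operative repair is required", and B2 that "ICP is rarely measured in patients with craniosynostosis".

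**The concern.** A2 can be tested only in children who have both an MRI measure and a direct ICP reading. The sections that decide who enters do not require the means of obtaining the direct reading, and the protocol's own background says it cannot be presumed in the population they recruit. A site that follows 2.a, 2.b and F1 exactly could fill the study with children who have no catheter. E1's transducer would then have nothing to attach to, and no later analysis can recover a reference measure that was never taken.

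The pilot's secondary use would suffer too. G1 says the data will guide the sample size of future studies, but without pairs there is no MRI-ICP correlation to plan from.

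**Working it through.** The plan has no derived figure to reproduce. G1 gives no power calculation, and neither the ten in A1 nor the 12 in E1 is justified. The check is therefore a comparison of sections, followed by a count.

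**1. Who is enrolled, and is a catheter secured?**

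| Section | Population | Shunt or catheter |
|---|---|---|
| A1 | Ten children with a shunt | Part of the definition |
| E1 | Up to 12 craniosynostosis patients, possibly controls | Presupposed, not stated as an entry condition |
| 2.a | Unrepaired single-suture cases; age-matched controls | Not mentioned |
| 2.b | Plastic Surgery clinic | Not mentioned |
| F1 | Craniosynostosis on CT | Not mentioned |

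A1 does not say that its ten children have craniosynostosis, and 2.a does not say that its cases have a shunt. No section states how the two groups overlap.

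**2. How many pairs can result?** There is a single visit, so count at most one pair per patient, and assume that controls supply no direct reading.

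- Planned under A1: 10 children × 1 = 10 pairs. This is a target.
- Maximum under E1's ceiling: 12 × 1 = 12 pairs.
- Minimum secured by 2.a, 2.b and F1: 0 patients required to have a catheter, so 0 pairs.

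The rules as written allow 0 to 12 pairs. The documents give no share of patients with a catheter, so no probability can be attached to any value in that range.

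**3. Do the counts conflict?** No: 10 ≤ 12, and E1's figure is a ceiling.

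**4. Is the direct reading scheduled?** E1 describes it; F2 does not list it.

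**5. Would the analysis test A2 if pairs existed?** No. G3/G4 name two comparisons (case against control, side against side), and neither relates an MRI measure to direct ICP. This gap is separate from eligibility and would remain after an eligibility fix.

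**6. Is the MRI half of the pair defined?** F4 lists NAA, lactate, oxygen extraction, cerebral blood flow, functional connectivity and optic nerve sheath size, among others. It does not say which is the indirect measure of ICP in A2. A catheter criterion would secure only the direct half.

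**7. Do the exclusions fit A1's children?** The criteria exclude implants that might rule out MR, and a history of other abnormalities affecting brain topology or function. Whether a shunt, or the condition that led to it, falls under either is not stated.

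**The case against.** The strongest defence is that the intent is clear. A1 names shunted children as the target, A2 depends on them, and E1 speaks of the catheter as present and of the direct reading without condition. On that view 2.a is merely incomplete, and investigators who know the aim would enrol accordingly. Part of this stands: E1 does presuppose a catheter, so the missing condition lies in 2.a, 2.b and F1. It does not settle the matter, because A1's shunt condition reaches no section that governs entry, and the population in 2.a is a different one, not a looser description of the same one.

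Some stronger readings are tempting, and the documents do not support them.

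- *The sample sizes contradict each other.* They do not; ten fits within a maximum of 12.
- *The study will yield no pairs.* Zero is the lower limit of what the entry rules permit, not a forecast. Any probability would rest on an invented catheter share.
- *A1 guarantees ten pairs.* It states a target. 2.d allows withdrawal at any time, and the MRI measure is not specified.
- *One or two parts proves that some patients skip the direct reading.* The sentence follows the text on controls, so one part may be meant for controls and two for patients.
- *The exclusions bar shunted children.* The wording leaves this open; it needs clarification only.
- *C1 also promises a comparison with direct ICP.* Its aim is "To evaluate ICP through the use of magnetic resonance (MR) imaging techniques in patients under the age of eight years old", which can be read descriptively.

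Pilot status does not answer the point. It explains the absence of a power calculation, not the absence of a rule securing the reference measure.

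**Conclusion.** The concern holds as an inconsistency between sections about the population, and it must be fixed. A1, A2 and E1 describe or need children in whom ICP can be read directly; 2.a, 2.b and F1 enrol children for whom this is not required, in a disease where the protocol itself says it is rare. The possible yield is 0 to 12 pairs, against ten planned. Separately, G3/G4 would leave A2 untested whatever the yield.

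The range rests on E1's ceiling, one pair per patient and no direct readings from controls. The conclusion needs no assumption about how many clinic patients have a catheter, about the significance level or about the size of the correlation; the documents give none of these.

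**What to change.** Reconcile the sections on one primary population. There are two coherent routes, and the choice is the sponsor's.

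**Route 1, to answer A2.**

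- In 2.a, require for the primary cohort an existing shunt or catheter from which ICP can be read, and state whether that cohort must also have craniosynostosis.
- Align 2.b and F1 with that criterion.
- Clarify how the implant and other-abnormality exclusions apply to shunted children.
- List in F2 the direct reading that E1 already describes.
- In G3/G4, name the correlation of one specified MRI measure from F4 with direct ICP as the primary analysis, and label the case-control and side-to-side comparisons descriptive.

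Cost: a protocol amendment and possibly a second recruitment source. It adds no procedure beyond those already in A1 and E1.

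**Route 2, if the craniosynostosis cohort is intended.** Revise A1, A2 and E1's catheter and transducer text, and A3 as needed, so that the study no longer claims a comparison with direct ICP.

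Cost: a protocol amendment and the loss of the validation against direct ICP.
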